# Introduction

## Dementia in the local community and impacts

Dementia is a syndrome describing a decline in memory and many other cognitive domains, and is associated with many neurodegenerative diseases, such as Alzheimer's disease (AD), vascular disease (for vascular dementia), etc. Mild cognitive impairment (MCI) is an intermediate state between normal cognitive aging and dementia, with a slight decline in memory and cognitive abilities compared to their counterparts. MCI is regarded as an intermediate state between normal cognitive aging and dementia, and the rates of conversion from MCI to dementia ranged from 6.0% to 44.8%, as reported in previous studies.

According to the World Health Organization (WHO), dementia is one of the major causes of disability and dependency in elderly people. The WHO reported that 2.1 billion people could live to the age of over 60 by 2050, and the number of people with dementia could rise to 139 million in 2050, compared to 55 million in 2019. In Hong Kong, about 1.2 million people currently live to the age of over 65, and about one-tenth of them are suffering from dementia. It is expected that almost one in three of our population will be aged 65 or above by 2041. Many elderly people with dementia live in nursing homes and elderly daycare centers. It poses a significant burden on caregivers, families, and the public healthcare system.

Until now, no interventions have been proven to totally cure dementia, and current drug therapies can only postpone its progression. For AD dementia, the Food and Drug Administration has approved several categories of medications, such as acetylcholinesterase inhibitors and N-methyl-D-aspartate (NMDA) receptor antagonists. For MCI and other dementia etiologies, pharmacological treatments are limited. The treatment of dementia should achieve different goals, not only slowing down cognitive deterioration but also improving patients' quality of life.

Patients with dementia not only have a wide range of cognitive impairments, including progressive memory loss, increasing difficulty in communication and language, concentration and attention, reasoning and judgment, but also develop a variety of frailty-related symptoms, mainly including physical and psychological frailty, such as musculoskeletal deterioration, neurological disorders, sleep, emotional, and even psychotic symptoms. Medical comorbidities in the elderly may limit their tolerance of medication. Management of dementia is sophisticated and has become a huge burden in future public healthcare systems.

The overall purpose of the management of dementia in the elderly is to reduce dementia- and frailty-caused adverse outcomes that increase disability, dependency, hospitalization, and long-term care admission. However, there is a dearth of effective interventions improving the quality of life of elderly with dementia. The development of holistic management strategies that not only prevent and slow down cognitive deterioration, but also reduce various other symptoms is therefore highly desired.

## Acupuncture and acupressure for dementia and elderly frailty-related symptoms

Acupuncture has been widely used in local clinical practice. Numerous studies have shown the benefits of acupuncture in reducing cognitive deterioration in patients with cognitive impairment and dementia and in animal models. Acupuncture is also effective in improving physical disability, rigidity, gait, and postural balance in aging adults with stroke and Parkinson's disease. A large body of evidence further confirms the effectiveness of various acupuncture regimens in treating pain, fatigue, sleep disturbance, anxiety, and depression. On the other hand, it is well demonstrated that, as a convenient therapy, acupressure has particular benefits in alleviating sleep disturbance, anxiety, depression, and agitation in elderly people with dementia. Acupressure also has positive effects on the recovery of motor function and the daily activities of stroke patients. These studies suggest that the elderly with dementia could benefit from acupuncture and acupressure.

## Our related studies

We have developed a novel acupuncture mode called comprehensive acupuncture therapy (CAT). CAT was built up from “dense cranial electroacupuncture stimulation (DCEAS)”, which consists of dense frontal acupoints with additional electrical stimulation, together with manual stimulation of multiple body acupoints selected based on previous clinical trials, the experience of acupuncture experts, and traditional Chinese Medicine (TCM) theory on the elderly’s constitutions. The efficacy of CAT has been well proven in our previous studies. Most recently, we have completed three clinical trials that evaluated the efficacy of acupuncture treatment for vascular dementia; stroke-caused cognitive deterioration, and chemotherapy-induced cognitive impairment. All these trials have consistently revealed that acupuncture is effective in alleviating cognitive impairment. Furthermore, our several studies have confirmed the efficacy of acupuncture in improving major depression; insomnia and anxiety; poststroke depression and movement disability.

Acupressure is a form of massage therapy involving the application of pressure to acupoints or specific body surfaces. We have developed a caregiver-performed acupressure protocol called ‘Comfy Acupressure for the Elderly (CAE)’ and a demonstration video is accessible at <https://www.youtube.com/watch?v=pAqNIZPKmnM>. CAE protocol was initially developed based on traditional Chinese Medicine theory and practice, with the aim of improving the quality of life and preventing aging and age-related conditions in the elderly. We have also shown the effectiveness of caregiver-performed acupressure on the general quality of life in frail older people, and self-administered acupressure for insomnia disorder.

These studies have led us to hypothesize that (1) CAT and CAE monotherapy could reduce cognitive impairment and related comorbid symptoms in aged people with dementia; and (2) CAT and CAE as a holistic intervention could produce additive effects than routine care in improving cognitive impairment, frailty-related disability and dependency, as well as comorbid symptoms in elderly people with dementia.

## **Hypothesis and aims to be tested**

Our hypothesis is that for the elderly with cognitive impairment or dementia, acupuncture and acupressure are feasible, safe, and could produce better management outcomes than routine care. The aims of this study are: (1) to determine whether the conditions of cognitive impairment in the treatment groups improve significantly when compared to control; (2) to determine whether other symptoms (e.g., functional independence, pain, depression, and sleep disorder) in the treatment groups improve more than in control; and (3) to investigate whether acupuncture or acupressure is safe for the elderly with cognitive impairment or dementia.

## **Plan of Investigation**

### Design

This is an assessor-blinded, randomized controlled trial. A total of 248 eligible subjects will be recruited from local nursing and care homes. They will be randomly assigned to either an acupuncture group (named the “comprehensive acupuncture therapy [CAT]” group), an acupressure group (named the “Comfy Acupressure for the Elderly [CAE]” group), a combined acupuncture and acupressure group (named the CAT+CAE group), or a control group (named the routine care group), with 62 subjects per group. Subjects assigned to the CAT, CAE, and CAT+CAE groups will respectively receive 2 sessions of CAT, 3 sessions of CAE, and a combination of both per week for 12 weeks. The primary outcome is the baseline-to-endpoint change in score of the Montreal Cognitive Assessment

(MoCA). Secondary outcomes include various domains of MoCA, functional independence, psychological well-being, sleep quality, and level of pain. A generalized linear mixed-effect model will be used to compare outcomes over time among the four groups. This trial has been approved by the Institutional Review Board of the University of Hong Kong/Hospital Authority Hong Kong West Cluster (Ref No.: UW 19-821). The study protocol has been registered at ClinicalTrials.gov (NCT04305951) before enrolment. The trial will be conducted in compliance with the protocol, the ethical principles of the Declaration of Helsinki and its subsequent amendment. The study flow chart is shown in [Figure 1](#).

## Subjects

### **Inclusion criteria**

Subjects will be eligible for this study if they: (a) are aged 65 years or above, (b) have a clinical diagnosis of any type of dementia or met the criteria of major and mild neurocognitive disorder based on the Fifth Edition of the Diagnostic and Statistical Manual of Mental Disorders (DSM-5); and (c) have mild to moderate dementia at a stage of 3 to 5 (Stage 3: mild cognitive decline; Stage 4: moderate cognitive decline/mild dementia; Stage 5: moderately severe cognitive decline/moderate dementia) on the Global Deterioration Scale.

### **Exclusion criteria**

Subjects will be excluded if they: (a) have the severity of dementia with a stage below 3 or above 5 on the Global Deterioration Scale; (b) have severe skin lesions on acupuncture and acupressure areas; (c) have a significant bleeding tendency; (d) have a heart pacemaker or implantable cardioverter defibrillator; (e) are currently receiving acupressure as a regular therapy; (f) had surgery on the head or neck; or (g) are currently receiving anti-coagulant treatment.

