### **Estimation of sample size**

Our recent study showed that CAT treatment for 8 weeks produced a  $2.3 \pm 2.8$  (SD) score greater improvement than control (minimum acupuncture stimulation, MAS) on MoCA in patients with poststroke cognitive impairment. One similar trial has reported that acupuncture treatment alone for 3 months yielded a  $1.9 \pm 4.1$  greater improvement than nimodipine, a commonly used anti-hypertension drug, on MoCA in patients with poststroke cognitive impairment. Based on these two trials, we expect that CAT could yield an average  $2.1$  [ $(2.3+1.9)/2 = 2.1$ ] score greater improvement on MoCA than routine care, with an average standard deviation (SD) equal to a 1.7-fold of mean difference [ $(2.8/2.3 + 4.1/1.9)/2 = 1.7$ ], i.e.,  $SD = 1.7 \times 2.1 = 3.6$ . The following formula is then used to further calculate the sample size:

$$n = \frac{2}{(M/SD)^2} \times C_{p,\text{power}}$$

where  $n$  is the number of subjects required in each arm and  $M$  is the mean difference that is equal to 2.1.  $SD$  is the standard deviation that is 3.6.  $C_{p,\text{power}}$  is equal to 7.9 when the two-tailed level of  $\alpha$  and power ( $1-\beta$ ) are set at 0.05 and 80%, respectively. It requires 62 subjects per arm, with an assumed dropout rate of 25%. We propose to recruit a total of 248 subjects ( $n = 62$  per arm for 4 arms).

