## **Treatment procedure**

(a) Routine care: All participants in the four groups will continue their current routine care and medications as usual. These routine cares will serve as covariates included in outcome analysis.

(b) CAT regimen: Subjects assigned to the CAT group will receive CAT treatment in addition to routine care. CAT will be conducted for 2 sessions per week for 12 consecutive weeks, a total of 24 treatment sessions. Registered Chinese medicine practitioners (CMPs) with a master's degree or above and with at least 5 years of acupuncture experience will be responsible for acupuncture treatment. A brief introduction to acupuncture procedures will be given by a CMP during the first visit. Details of selected acupoints are illustrated and summarized in [Figure 2](#) and [Table 1](#).

The acupuncture treatments will be conducted at the subjects' corresponding care homes. Each subject will receive a maximum of 26 needles per treatment session, adjusted by their tolerance, in a supine position. The following 14 body acupoints with only manual stimulation will be used: Shenmen (HT7, 神門), Hegu (LI4, 合谷), Waiguan (TH5, 外關), Zusani (ST36, 足三里), Fenglong (ST40, 豐隆) and Sanyinjiao (SP6, 三陰交) on both sides, and Zhongwan (CV12, 中脘) and Guanyuan (CV4, 關元) in the midline. Meanwhile, electrical stimulation will be conducted on six pairs of frontal acupoints with positive (+) and negative (-) electrode cord connections as follows: Baihui (GV20, 百會) and Yintang (EX-HN3, 印堂), left Sishencong (EX-HN1, 四神聰) and Toulinqi (GB15, 頭臨泣), right Sishencong (EX-HN1, 四神聰) and Toulinqi (GB15, 頭臨泣), bilateral Shuaigu (GB8, 率谷), bilateral Taiyang (EX-HN5, 太陽), and bilateral Touwei (ST8, 頭維).

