### **Control group**

The group that receives routine care only will serve as the control group. For acupuncture, sham acupuncture techniques such as Streitberger needle may not be suitable for elderly subjects as they are associated with an increased risk of skin injury. Also, sham acupuncture has been proved not to be an inert method. For acupressure, the CAE regimen involved multiple steps like pressing and kneading different body parts. Typical sham acupressure procedures, like using a non-acupoint or placebo acupressure device, are not applicable for the CAE treatment.

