### **Data processing and analysis**

One biostatistician who is blinded to interventions will be responsible for statistical analysis. The analysis will be carried out on the intention-to-treat (ITT) population, for which participants have been randomized. A linear mixed-effect model will be applied to compare the primary outcome (changes in total MoCA score from baseline) and secondary outcomes (changes in scores of the Digit span test, MBI, VAS, GDS and ISI), with time (baseline, week 6, and week 12) and group (CAT, CAE, CAT+CAE, and routine care) as categorical fixed factors and random intercepts within a scaled identity covariance matrix. Gender, age, baseline MoCA score, and baseline medication will serve as covariates. Subgroup analysis will be further conducted to compare outcomes by gender, age, and severity of dementia to detect whether these factors are associated with the outcomes. Pairwise comparisons will be further carried out to examine between-group differences. One-way analysis of variance (one-way ANOVA) will be used to detect differences in continuous baseline variables. Categorical baseline variables, including discontinuation and incidence of AEs, will be analyzed using the Chi-square test or Fisher's exact test. Statistical significance was defined as a two-tailed  $P < 0.05$ . The analysis will be conducted using R Studio software.

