- (c) Marital status (Categories: married or living with partner / single, separated, divorced, or widowed)
- (d) Education level (Categories: uneducated / primary or below / lower secondary / upper secondary / university or above)
- (e) Past occupation (Categories: managers and administrators / professional and associate professional / skilled and semi-skilled worker / unskilled worker / housework / others)
- (f) Type of cognitive impairment (Categories: Alzheimer's disease / vascular dementia / others)
- (g) Past medical history (Categories: cardiometabolic disease / malignant neoplasm / stroke / Parkinson's disease / psychotic disorder / affective disorder)
- (h) Current medication (Categories: cholinesterase inhibitors / glutamate regulators / antidepressants / antipsychotics / hypnotics)

- (i) Baseline MoCA score
- (j) Baseline DSF and DSR scores
- (k) Baseline MBI score
- (l) Baseline VAS score
- (m) Baseline GDS-15 score
- (n) Baseline ISI score

Continuous variables will be presented using mean with standard deviation (SD). One-way analysis of variance (one-way ANOVA) will be used to detect differences in continuous baseline variables.

Categorical variables will be presented by counts with percentages. Percentages will be calculated according to the number of patients for whom data are available. Categorical variables will be analyzed using the Chi-square test or Fisher's exact test.

Discontinuation will be summarized by counts with percentages. Chi-square test or Fisher's exact test will be used to detect differences between the four groups.

Primary outcome

A linear mixed-effect model will be applied to compare the primary outcome (changes in total MoCA score from baseline), with time (baseline, week 6, and week 12) and group (CAT, CAE, CAT+CAE, and routine care) as categorical fixed factors and random intercepts within a scaled identity covariance matrix. Gender, age, baseline MoCA score, and baseline medication will serve as covariates. Pairwise comparisons will be further carried out to examine between-group differences. Two-tailed P-values will be reported in addition to confidence intervals ([Proposed Tables 2 and 3](#)).

Subgroup analysis will be further conducted to compare outcomes to detect whether these subgroup factors are associated with outcomes. The following subgroups include:

- (a) Age (<85 years and \geq 85 years);
- (b) Gender (male and female); and

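### Exclusion criterion (e) bars current regular acupressure but not current regular acupuncture, and the plan names no variable that would record outside acupuncture

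*Protocol*

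**What the plan says.** Protocol, Exclusion criteria, item (e), removes people who "are currently receiving acupressure as a regular therapy". The SAP's exclusion list has the same item. None of items (a) to (g) in either document mentions current or recent acupuncture.

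On background care, Protocol, Treatment procedure (a), states: "All participants in the four groups will continue their current routine care and medications as usual". It adds: "These routine cares will serve as covariates included in outcome analysis". The SAP's Intervention section repeats both statements. Protocol, Control group, defines the comparator: "The group that receives routine care only will serve as the control group". No section of either document rules out outside acupuncture during the 12 weeks.

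On the analysis, Protocol, Data processing and analysis, says: "Gender, age, baseline MoCA score, and baseline medication will serve as covariates". The SAP gives the same list for the primary and the secondary outcomes. The SAP's baseline comparisons describe background treatment only as "Current medication (Categories: cholinesterase inhibitors / glutamate regulators / antidepressants / antipsychotics / hypnotics".

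On how common acupuncture may be, the protocol's background section says: "Acupuncture has been widely used in local clinical practice".

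**The concern.** Screening out current acupressure users shows that the sponsor saw prior exposure to a study modality as a problem. The same safeguard is not applied to the other modality, and no reason is given. A resident on regular acupuncture is eligible, can be allocated to routine care or CAE, and may carry on with it.

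The stake is the contrast for which the trial was sized, CAT versus routine care, where the protocol's $M$ "is the mean difference that is equal to 2.1". CAT+CAE versus CAE is exposed in the same way, and it bears on the SAP's hypothesis that the combination does better than either treatment alone. If some participants in both arms of such a contrast already receive acupuncture, and CAT does less for them than for others, the average difference falls. Since the plan names no variable for this use, the report could neither say how many participants were affected nor adjust for them.

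**Working it through.** **Inputs from the documents.** Difference M = 2.1, SD = 3.6, two-tailed α = 0.05, power 80%, multiplier C = 7.9, dropout 25%, 62 per arm (Protocol, Estimation of sample size; SAP, Sample size determination). Allocation is 1:1:1:1 (Protocol, Randomization, central allocation and blindness).

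**Inputs assumed here.** f is the share of participants already on regular acupuncture. It is not in the documents, and 5%, 10% and 20% are used for illustration. λ is the fraction of CAT's effect that is lost in such a participant: 0 if the effects are fully additive, 1 if CAT adds nothing (full overlap). λ is not in the documents either.

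**Step 1. The plan's own figure.** n = 2C/(M/SD)² = 2 × 7.9/(2.1/3.6)² = 46.43 per arm. Dividing by 0.75 gives 61.9, so 62. The stated size reproduces. With 25% dropout, 62 × 0.75 = 46.5 completers per arm, and a two-sample t-test then has about 79% power (79.5%). The normal approximation gives 80.3%. There is little slack.

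**Step 2. What dilution requires.** Randomization spreads users over all arms, so the expected share is f in each. In CAT versus routine care, non-users (share 1 − f) contribute the full 2.1 and users contribute 2.1 × (1 − λ). The expected contrast is

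2.1 × (1 − f) + 2.1 × (1 − λ) × f = 2.1 × (1 − λf).

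The mere presence of users in the control arm does not reduce it; λ must exceed zero. The same expression applies to CAT+CAE versus CAE, with the CAT increment in place of 2.1. In CAE versus routine care neither side receives CAT, so background acupuncture matters there only if it interacts with acupressure.

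**Step 3. Numbers.** Two-sample t-test, SD 3.6, 46.5 per arm:

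| Share f | No overlap (λ = 0) | Half overlap (λ = 0.5) | Full overlap (λ = 1) |
|---|---|---|---|
| 5% | 2.10, 79% | 2.1 × 0.975 = 2.05, 77% | 2.1 × 0.95 = 2.00, 75% |
| 10% | 2.10, 79% | 2.1 × 0.95 = 2.00, 75% | 2.1 × 0.90 = 1.89, 71% |
| 20% | 2.10, 79% | 2.1 × 0.90 = 1.89, 71% | 2.1 × 0.80 = 1.68, 61% |

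The normal approximation puts the full-overlap column at 76%, 72% and 61%.

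**Step 4. Would the planned analysis see it?** The statement that routine care will be a covariate could in principle cover acupuncture. The models, however, name gender, age, baseline MoCA and baseline medication, and the SAP's medication variable consists of five drug classes. The SAP's proposed Table 1 and the protocol's Table 3 schedule have no entry for acupuncture. The general statement is not carried into any named variable.

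**The case against.** A reader might infer that controls are receiving CAT and that the trial is therefore biased toward no effect. The documents do not support that, for four reasons.

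First, users are expected equally in all arms, so the contrast is unchanged unless CAT adds less for them. The full-overlap column is a bound, not an expectation.

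Second, CAT is a specific regimen: electrical stimulation of six pairs of frontal acupoints with 14 body acupoints, over 24 sessions. Outside acupuncture of unknown type, frequency and indication is not CAT, and nothing in the documents gives it CAT's effect.

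Third, the remark about local use concerns clinical practice in general, not nursing- and care-home residents at Global Deterioration Scale stages 3 to 5. The share could be close to nil.

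Fourth, the outcome is change from baseline. A resident already on acupuncture may have any benefit in the baseline score, so a fresh 2.1-point gain in routine care should not be assumed.

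All four limit the size of the concern, and the first three stand in full. The fourth rules out one route to dilution but not overlap: if CAT adds nothing for users, they contribute no difference whether their benefit came before baseline or after it.

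It can also be said that the plan intends to adjust for routine care, and that the case record form is to record each participant's treatment. Neither closes the gap, because no acupuncture item is described and the model's covariate list does not include one.

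**Conclusion.** The gap is real and appears in both documents: one tested modality is screened for and the other is not, and following the plan as written can admit and retain acupuncture users without recording them. Its effect is unknown and may be zero. For an assumed share of 5% to 20%, the 2.1-point contrast lies between 2.1 (about 79% power) and, under full overlap, 2.00 to 1.68 (75% to 61% power). These figures rest on the plan's SD of 3.6, on 46.5 completers per arm, and on shares and overlap that the documents do not supply.

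The stated sample size is not in error, and a definite bias is not shown. This is a low-cost improvement that protects the contrast for which the trial was sized, not a challenge to the trial's validity.

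**What to change.** 1. In criterion (e) of both documents, insert *acupuncture or* before *acupressure*, so that current regular use of either is an exclusion. If the sponsor means the two to be treated differently, state the reason.
2. For participants already enrolled, record acupuncture use at baseline, from care records or recall, and during the 12 weeks. Report both by arm.
3. Add a sensitivity analysis that repeats the primary comparison without baseline users. Define the subset by baseline use only: use that starts after randomization may depend on the arm, and dropping those participants would break the randomized comparison.
4. Reconcile the statement that routine care will be a covariate with the model's covariate list, either by naming the variables or by withdrawing the statement.

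The planned 62 per arm does not change, because the sample-size inputs do not change. The cost is a short amendment, one extra data item and a slightly smaller eligible pool. Baseline use reconstructed from records or recall will be imperfect, and the sensitivity analysis will have fewer participants, so it should be read as supportive.
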